## **GLOSSARY OF ABBREVIATIONS**

## KEYWORDS

Stroke, Arm Rehabilitation, Neurology, Behaviour, Usability, Design

## STUDY SUMMARY

**TITLE** Usability study of OnTrack Tools: a study to assess the usability of a clinician-facing software application to support arm rehabilitation after stroke.

**DESIGN** A usability study of the OnTrack Tools graphical user interface (GUI) using a combination of qualitative and quantitative methods. The evaluation of the GUI will be divided into three phases of evaluation.

**AIMS** assess the usability of the OnTrack Tools GUI under simulation by therapists managing the rehabilitation of stroke survivors.

**OUTCOME MEASURES** The usability of the intervention will be evaluated at each of the three phases using standardised questionnaires on usability such as the System Usability Scale (SUS), the Post-Study System Usability Questionnaire (PSSUQ), and the Usefulness, Satisfaction, and Ease of Use Scale (USE)., In addition, a focus group will be conducted at the end of each testing phase to record feedback from participants.

**POPULATION** Occupational Therapists and Physiotherapists working in the stroke wards at ICHT.

**ELIGIBILITY** Participants will be adult (18 years old or over) Occupational Therapists and Physiotherapists (Band 4 to Band 8) working in the stroke wards at ICHT. No exclusion criteria has been defined.

**DURATION** 3 months

## 1. INTRODUCTION

### 1.1. BACKGROUND

Arm disability following a stroke affects 450,000 people in the UK, equating to 77% of stroke patients with a disability. Arm recovery after stroke is a national research priority, yet a recent Cochrane review of over 500 trials failed to yield high-quality practice recommendations (Pollock, 2014).

The gold-standard of care is dose-intensive repetitive rehabilitation (CQC, 2011). However, NHS resources are limited and unable to provide this. There is untapped potential to increase repetitive rehabilitation by targeting the 90% of the day where patients are going about their daily activities and can use their arm movement (however small) to a greater extent.

The OnTrack rehabilitation system has been designed to track arm activity throughout the day and provide tailored support from clinicians. A feasibility study in the NHS has shown promising outcomes ([name], 2020). Participants (n=12) found OnTrack beneficial and reported improved confidence when performing activities. Preliminary results have also shown a 64% increase in arm activity and 18% increase in arm performance on average after 12 weeks of using OnTrack. Trial registration: NCT03944486.

### 1.2. RATIONALE FOR CURRENT STUDY

This study aims to assess the usability of the OnTrack Tools GUI under simulation. The study follows up from a study of the OnTrack system that demonstrated the feasibility and acceptability of the patient-facing component of the system by stroke survivors and therapists. The design of this study was developed through a collaborative approach between the study researchers, patients, and front-line therapists.

## 2. STUDY OBJECTIVES

Primary outcome: To assess the usability of the OnTrack Tools GUI under simulation by therapists managing the rehabilitation of stroke survivors.

Secondary outcomes: To understand aspects of the GUI that could improve as well as additional features that could be implemented in future development.

### 3. STUDY DESIGN

Usability study of OnTrack Tools: a study to assess the usability of a clinician-facing software application to support arm rehabilitation after stroke.

#### Study Design

A usability study of the OnTrack Tools graphical user interface (GUI) using a combination of qualitative and quantitative methods. Usability can be defined as the measure of the effectiveness of interaction between users and the system; in other words, how users perform tasks using the system.

Testing will be performed in three phases by target end-users - stroke therapists (occupational therapists and physiotherapists) - recruited from Imperial College Healthcare NHS Trust.

#### Outcomes

The usability of the OnTrack Tools system will be evaluated at each of the three phases using standardised questionnaires on usability such as the System Usability Scale (SUS), the Post-Study System Usability Questionnaire (PSSUQ), and the Usefulness, Satisfaction, and Ease of Use Scale (USE). Questionnaires will be administered online using Qualtrics on the devices that will be loaned to the participants for the study. In addition, a focus group will be conducted at the end of each testing phase to record feedback from participants. Focus groups will be face-to-face wherever possible and will take place at Charing Cross Hospital in the CNRU or ASU gyms, both of which are on the 9th floor and accessible to all therapists. Covid guidance will be followed. If a session needs to be moved online, it will be done using Microsoft Teams. Focus group sessions may be audio recorded using a recording device and photos/video may be taken with participant consent. Audio recordings may be sent to an external party (PageSix Transcription Services Ltd) for transcription, recordings will be deleted after transcription.

#### Intervention

The intervention is the OnTrack Tools system consisting of a GUI used to manage patients who are users of the OnTrack rehabilitation system. Participants will be asked to complete clinical and non-clinical tasks in simulation using OnTrack Tools. The themes for the scenarios of use presented in each of the three phases are summarised below:

Phase 1 - Account creation, system onboarding and general system navigation.

Phase 2 - Individual patient management.

Phase 3 - Content and data management.

#### Recruitment

Occupational Therapists and Physiotherapists will be recruited from Imperial College Healthcare NHS Trust (ICHT). A Research Therapist (RT) working on site will be responsible

for identifying and recruiting participants. They will introduce the study to potential participants and provide information documents allowing a minimum of 24 hours for potential participants to formulate questions. The RT will be able to answer questions or will liaise with the project lead to provide an answer. Once all questions are answered and a potential participant is happy to participate, consent will be taken by the RT. The study aims to recruit 5-10 therapists per evaluation phase, this equates to 30-50% of Band 4 to Band 8 therapists at ICHT. Given the rotational nature of therapist work at ICHT, we expect different participants taking part at each of the three phases of evaluation.

## **Study duration**

3 months

## **4. PARTICIPANT ENTRY**

### **4.1. PRE-REGISTRATION EVALUATIONS**

There will be no pre-registration evaluations necessary for eligible participants to be included in the study.

### **4.2. INCLUSION CRITERIA**

Adult (18 years old or over) Occupational Therapists and Physiotherapists (Band 4 to Band 8) working in the stroke wards at ICHT.

### **4.3. EXCLUSION CRITERIA**

No exclusion criteria has been defined.

### **4.4. WITHDRAWAL CRITERIA**

Participants are free to withdraw from the study at any time. However, anonymised activity data collected may still be used for data analysis as this is unlinked of any participant identifiable information.

Participants will be able to withdraw from the study by contacting the research team in person or in writing via the contact details provided in the participant information sheet.

## **5. ASSESSMENT AND FOLLOW-UP**

There will be no follow-up after the third round of evaluation. Data collection for the study and participants' involvement will end at this point.

## **6. STATISTICS AND DATA ANALYSIS**

### **Sample size**

15 participants over three cycles of evaluation.

Nielsen, et.al. (1993) advocate that a sample size of 5 participants over 3 rounds of testing will be able to uncover close to 100% of all usability problems. Taking into consideration the staffing numbers at ICHT, we anticipate being able to recruit a

maximum of 10 participants per round and expect a 50% drop out or non-completion rate.

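### Under the plan's own 50% loss, the stated size of 15 is expected only if every phase recruits its maximum of 10, but the stated aim is to recruit 5-10

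*Combined protocol and SAP*

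**What the plan says.** Section 6 (Sample size) gives the size as "15 participants over three cycles of evaluation". The support is a cited usability-testing source, from which the plan takes that "a sample size of 5 participants over 3 rounds of testing will be able to uncover close to 100% of all usability problems". The same section then turns to feasibility. Given staffing, the team anticipates a "maximum of 10 participants per round and expect a 50% drop out or non-completion rate".

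Section 3 (Recruitment) states the aim per phase: "The study aims to recruit 5-10 therapists per evaluation phase, this equates to 30-50% of Band 4 to Band 8 therapists at ICHT". It adds that, because therapists rotate, "we expect different participants taking part at each of the three phases of evaluation".

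Neither section says whether 15 counts people recruited or people who complete, and no section sets a minimum number completing per phase.

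**The concern.** The expected loss appears in section 6 but is not carried into the recruitment aim in section 3. With half of the recruits expected not to complete, an aim whose lower end is 5 recruits cannot be expected to yield 5 completing. The rule of 5 participants over 3 rounds is the only justification given for the size, so a reader needs to know whether the recruitment aim is expected to deliver it.

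As written, every phase could meet its recruitment aim and the study could still expect well under 15 to complete. A reader of the final report, seeing for example 8 therapists with complete data, could not say whether the plan had been met or missed.

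**Working it through.** **Inputs**
- Size: 15 in total, from 5 per round and 3 rounds (section 6).
- Maximum recruits per round: 10 (section 6).
- Expected drop-out or non-completion: 50% (section 6).
- Recruitment aim: 5 to 10 per phase (section 3).
- Different people expected in each phase (section 3), so the phase numbers are added.

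**Reproducing the plan's figure**
- From the cited rule: 5 x 3 = 15.
- From the maximum and the loss: 10 x (1 - 0.5) x 3 = 15 completing.

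Both routes give 15. The second works only with 15 read as completing and recruitment at its maximum in every round.

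**Applying the same loss to the aim in section 3**

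For n recruits per phase, the expected number completing is n x 0.5 per phase and n x 0.5 x 3 in total. The largest loss that still leaves 5 completing is 1 - 5/n.

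| Recruits per phase | Expected completing per phase | Expected completing in total | Largest loss leaving 5 |
|---|---|---|---|
| 5 | 2.5 | 7.5 | 0% |
| 6 | 3 | 9 | 17% |
| 7 | 3.5 | 10.5 | 29% |
| 8 | 4 | 12 | 38% |
| 9 | 4.5 | 13.5 | 44% |
| 10 | 5 | 15 | 50% |

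Working backwards, 5 completing at 50% loss needs 5 / 0.5 = 10 recruits per phase, or 30 over three phases. Within the aim, only 10 absorbs the stated loss.

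**How firm 15 is at the maximum**

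Even with 10 recruits, 5 is an expected number and not an assured one. As an illustration, suppose each recruit is lost independently with probability 0.5. The chance of at least 5 completing out of 10 is then 0.623, and the chance that all three phases reach 5 is 0.623 cubed, about 0.24. The independence assumption is mine, and the conclusion does not depend on it.

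**The case against.** The strongest reply is that section 6 is coherent. Its two routes to 15 agree, which points clearly to 15 meaning completing. The range in section 3 contains the required 10, and its ends match section 6's own figures, so it may be shorthand for 5 needed and up to 10 recruited. The study is also formative, with no hypothesis test.

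Most of this stands. There is no arithmetic error, and the fault lies in how the two sections connect. The shorthand reading is possible but does not settle the matter. Section 3 uses the word recruit, and it converts the whole range into a share of the staff ("this equates to 30-50% of Band 4 to Band 8 therapists at ICHT"), which treats both ends as people drawn from the pool. Read that way, the lower end makes no allowance for the loss.

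A reader might infer three stronger points that the documents do not support:
- **That 15 means recruited, so that only 7.5 are expected to complete.** This would require section 6 to name 10 recruits per round and a 50% loss and then ignore both. It is a weak reading and should not be given equal weight.
- **That people who drop out still supply enough data to close the gap.** Section 4.4 says only that "anonymised activity data collected may still be used for data analysis". It does not mention the questionnaires or focus groups by which usability is evaluated, and it does not equate withdrawal with the non-completion in section 6. No count of contributors can be built on it.
- **That the discovery claim fails in any single phase with fewer than 5.** The plan states the claim for 5 participants over 3 rounds and gives no cut-off for a single phase.

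**Conclusion.** The point holds as a minor inconsistency between section 3 (Recruitment) and section 6 (Sample size). At the plan's 50% loss, the stated aim gives an expected 2.5 to 5 completing per phase and 7.5 to 15 in total. The stated 15 is reached in expectation only at the ceiling, with no margin. With 5 to 9 recruits per phase, the aim is met but only 2.5 to 4.5 are expected to complete.

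This rests on three assumptions:
- The 5 per round means people who actually complete testing. That is the natural reading of the justification but is not stated.
- The 50% applies equally to each phase.
- The participants in each phase are different people, as the plan expects.

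The effect on the share of usability problems found cannot be quantified, because the documents give no detection rate per participant. With no decision rule in the plan, no conclusion of the study fails because of this.

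**What to change.** Reconcile the two sections by wording alone:
1. Label 15 in section 6 as participants completing, and 5-10 in section 3 as participants recruited.
2. Restate the size as about 8 to 15 expected to complete in total (7.5 rounded up) for 5 to 10 recruits per phase, with 15 the expected number only if every phase recruits 10.
3. Tie the near-complete discovery statement to the 5 participants over 3 rounds on which it rests, and do not present it as met if fewer than that complete. This does not imply that the statement is established once that number is reached.

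The cost is a less favourable stated size. No extra recruits and no new outcomes are needed.

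Committing to 10 recruits per phase would also close the gap, but that is a recruitment decision for the study team and is not needed for this fix. It would mean 30 different people. If section 3's 30% is paired with 5 and its 50% with 10 (my assumption), the staff pool at any one time is about 17 to 20 (5 / 0.30 = 16.7; 10 / 0.50 = 20), so that route would depend on staff rotation.

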### **Data analysis**

Analysis will be completed on the parameters of usability of the intervention, including the quantitative results of outcome measures and the qualitative outputs from focus groups.

Data and all appropriate documentation will be stored for a minimum of 10 years after the completion of the study.

## **7. REGULATORY ISSUES**

### **7.1. ETHICS APPROVAL**

The Study Coordination Centre has obtained approval from the Health Regulatory Authority (HRA). The study must also receive confirmation of capacity and capability from each participating NHS Trust before accepting participants into the study or any research activity is carried out. The study will be conducted in accordance with the recommendations for physicians involved in research on human subjects adopted by the 18th World Medical Assembly, Helsinki 1964 and later revisions.

### **7.2. CONSENT**

Consent to enter the study must be sought from each participant only after a full explanation has been given, an information leaflet offered and time allowed for consideration. Signed participant consent should be obtained. The right of the participant to refuse to participate without giving reasons must be respected. All participants are free to withdraw at any time from the study without giving reasons and without affecting their role as a member of staff.

### **7.3. CONFIDENTIALITY**

The Chief Investigator will preserve the confidentiality of participants taking part in the study and is registered under the Data Protection Act.

Data will be pseudonymised.

Researchers will have participants' names, contact numbers, and/or emails for the purposes of managing the study. This information will be stored securely as per Imperial College London data policy.

Participants will be assigned an identification number that will be used in place of their name wherever possible.

The document that links the participant's name to their ID number will be stored on a password protected university computer.

Images, videos and audio recordings may be taken at any stage of the study with the participants' consent. Media will be stored securely on a password protected device owned by the sponsor. Audio recordings may be transcribed by an external service (with contractual

arrangements with the sponsor) - with participant identifiable information removed ahead of this, recordings will be deleted after transcription. Photographs taken will be anonymised as soon as possible. Videos will exclude participants' faces.

Direct quotes may be used alongside a participant characteristic (e.g. Occupational Therapist, Band 5) however participant identifiable information will not be used alongside quotes.

There will be a combination of participant information stored on paper (e.g. consent forms) and electronically (e.g. contact details). Paper documentation will be stored in a locked cupboard inside a locked office at ICL or ICHT only accessible to the researchers. Electronic information will be stored on password protected university computers.

#### **7.4. INDEMNITY**

Imperial College London holds negligent harm and non-negligent harm insurance policies which apply to this study.

#### **7.5. SPONSOR**

Imperial College London will act as the main Sponsor for this study. Delegated responsibilities will be assigned to the NHS trusts taking part in this study.

#### **7.6. FUNDING**

SBRI Healthcare is funding this study. No participant payments or incentives will be provided.

#### **7.7. AUDITS**

The study may be subject to audit by Imperial College London under their remit as sponsor and other regulatory bodies to ensure adherence to GCP and the UK Policy Frame Work for Health and Social Care Research.

### **8. STUDY MANAGEMENT**

The day-to-day management of the study will be co-ordinated through the Helix Centre by [name] (contact details above).

### **9. PUBLICATION POLICY**

The researchers will seek to publish their work through publications in peer-reviewed journals.

